Study staff will conduct focus group discussions (one at each intervention health center) with all eligible providers at least 12 months after randomization. The focus group discussions will assess fidelity and barriers to uptake of each intervention component. Focus group discussions will be conducted by trained and experienced staff, audio-recorded, and professionally transcribed.

[figure not shown]
Assessment of patient's vital status, diagnostic and treatment status, HIV status, and ART status

Study staff will call all eligible patients included in the study 6 months after their initial health center visit to assess vital status, diagnostic and treatment status, HIV status, and ART status (if the patient is HIV-infected). Staff will call phone numbers recorded in the lab register, Xpert referral form and/or TB treatment register. For participants who cannot be reached, staff will make up to two additional phone calls on successive days. If the participant or a family member cannot be reached by telephone, study staff will work with a community health worker from the health center at which the participant underwent TB testing to conduct a home visit (using the address recorded in the lab register, Xpert referral form and/or TB treatment register). In addition to tracing efforts, staff will review TB treatment register data to ascertain vital status for participants who cannot be reached by phone but are known to have initiated TB treatment.

Provider interviews

Study staff will conduct in depth semi-structured interviews with 20-30 (2-3 per site) eligible providers to understand reasons for variability in uptake and effectiveness of the intervention strategy after completion of the trial. Health workers will be sampled purposively (*i.e.*, from low- and high-performing sites). Interviews will be conducted by trained and experienced staff, audio-recorded, and professionally transcribed.

Figure 3. Site visit activities

* At intervention health centers, GeneXpert I will be replaced with GeneXpert Omni once Omni is available at a regularly scheduled post-randomization visit. Lab staff will receive training on use of GeneXpert Omni and the solar panel used to power the GeneXpert I instrument will be removed.

Outcomes

Definitions

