2.3 General comments

Trial reporting will follow the Standards for Reporting Implementation Studies (STaRI) checklist to evaluate the trial's coprimary aims: clinical effectiveness and implementation of onsite Xpert testing.¹ In addition, reporting will include elements from the CONSORT 2010 extension checklist for cluster randomized trials, such as the randomization process and a participant flow diagram.²

This Statistical Analysis Plan summarizes analyses for all effectiveness outcomes, including the primary outcome of the number of patients treated for microbiologically-confirmed TB within 14 days of referral for sputum-based testing. Secondary outcomes for **testing** (number and proportion of patients completing TB testing), **diagnosis** (number and proportion diagnosed with microbiologically-confirmed TB, number and proportion diagnosed with RIF-resistant TB, time to microbiologically-confirmed TB), **treatment** (number and proportion treated for TB, time to treatment of microbiologically-confirmed TB), and **follow-up** (number and proportion with microbiologically-confirmed TB completing treatment, number and proportion who died within 6 months) will also be assessed. These endpoints will be evaluated through review of TB registers and GeneXpert machine data for all patients initiating TB evaluation at participating health centers.

This Statistical Analysis Plan is written in support of and is predominantly consistent with the full trial protocol; however, this analysis plan takes precedence.

3. Trial Summary

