3.4 Outcomes

Definitions used to assess study outcomes

- **Eligible patient:** clinic attendees satisfying our inclusion and exclusion criteria (as listed above) AND excluding patients aged <18 years or those with a documented prior history of TB treatment (e.g., reason for Xpert testing or TB treatment marked as treatment failure, relapse, treatment after loss to follow-up, etc.). In addition, patients identified as RIF resistant by Xpert testing will not contribute to the primary and secondary analysis except for the number and proportion with RIF resistance detected by Xpert or RIF resistance confirmed by culture.
- **Number enrolled (i.e., number evaluated for TB):** Number of eligible patients identified over a defined enrolment period through review of the NTLP Presumptive TB register, NTLP Laboratory register, GeneXpert laboratory requisition forms and NTLP Treatment register at each study site (includes patients treated for TB without undergoing any sputum testing).
- **Date enrolled:** Earliest date recorded in the NTLP Presumptive TB register, NTLP Laboratory register, GeneXpert laboratory requisition form, NTLP Treatment register or machine data. Records will be prospectively reviewed using name, sex, and age to identify patients presenting multiple times over the study period. Visits occurring within six months of enrollment will be considered as part of the same episode.
- **Number referred for testing:** Number of eligible patients identified through review of the NTLP Presumptive TB register, NTLP Laboratory register and GeneXpert laboratory requisition forms at each study site. Patients indicated as new in the NTLP Treatment Register will also be considered testing referrals.
- **Number tested:** Number of eligible patients with any smear or Xpert result entered into the NTLP Presumptive TB register, NTLP Laboratory register, GeneXpert laboratory requisition forms, or NTLP treatment register at each study site, or with a test result recorded in the onsite GeneXpert machine. Results must be dated within six months of enrolment. If result date is missing and cannot be found in the GeneXpert machine data, it will be assumed that the patient was tested within six months of enrolment.

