- **Number treated:** Number of eligible patients entered into the NTLP Treatment register as having started Category I or II regimen.
- **Number completing treatment:** Number treated and with a treatment outcome of cured or completed entered into the NTLP Treatment register.
- **Number died, among those initiated on TB treatment:** Number treated and with a treatment outcome of died entered into the NTLP Treatment register within six months of enrolment , or number treated and confirmed dead by next of kin with a date of death within six months of enrolment.
- **Number died, among those with confirmed TB:** Number diagnosed and with a treatment outcome of died entered into the NTLP Treatment Register within six months of enrolment, or number diagnosed and confirmed dead by next of kin with a date of death within six months of enrolment.
- **Number died, among all those eligible:** Number treated and with a treatment outcome of died entered into the NTLP Treatment register within six months of enrolment, or number traced with a death recorded
- **Time-to-diagnosis:** Number of days from *date enrolled* to earliest date of positive smear or valid Xpert result recorded in NTLP Presumptive TB register, NTLP Laboratory register, GeneXpert laboratory requisition form, or NTLP treatment register within six months of enrolment . For the control arm, attempts will be made to abstract the missing Xpert result dates from machine data from GeneXpert machines at testing hubs. For patients with microbiologically confirmed TB who are missing the smear or Xpert result date, the date of treatment initiation will be used as the date of diagnosis.
- **Time-to-treatment:** Number of days from *date enrolled* to treatment start date entered into NTLP Treatment register if treatment start date is within six months of enrolment.

Primary Outcome

Outcome	Numerator	Denominator
Number treated for microbiologically-confirmed TB within 14 days of date enrolled.	Number diagnosed and time-to-treatment within 14 days	None

Secondary Outcomes

A. Testing		
Outcome	Numerator	Denominator
Number referred for TB testing	Number referred for testing	None
Proportion completing testing	Number completing testing	Number enrolled
B. Diagnosis		
Outcome	Numerator	Denominator
Number diagnosed with microbiologically-confirmed TB*	Number diagnosed	None
Proportion diagnosed with microbiologically-confirmed TB*	Number diagnosed	Number enrolled

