The minimum detectable effect size is based on published literature, our preliminary data demonstrating the increased sensitivity of Xpert Ultra vs. smear microscopy (95% vs. 40%), and reduced pre-treatment loss to follow-up expected in the intervention vs. control arms due to rapid, onsite molecular testing (7% vs. 30%). When applying these parameters to a population of 1000 individuals with TB prevalence of 10%, we would expect 95 patients to be diagnosed with TB and 88 to start treatment within 14 days in the intervention arm, and 40 patients to be diagnosed with TB and 28 to start treatment within 14 days in the control arm. Thus, the expected difference in the primary outcome proportion would be 8.8% vs. 2.8%, or 6%.⁸

Table 1. Absolute difference in the proportion of clinic attendees initiating TB treatment within 14 days of initial sputum submission, among those referred for TB testing

Average cluster size	Effect size (10 clusters per arm, $k=0.36$)		
	80% Power	85% Power	90% Power

178 (12 months)	5.9%	6.5%	7.4%
223 (15 months)	5.7%	6.3%	7.1%
268 (18 months)	5.5%	6.1%	6.9%
312 (21 months)	5.4%	6.0%	6.7%
357 (24 months)	5.3%	5.9%	6.6%

Figure 1. Effect size by cluster size. Number of clusters per arm is 10, $k=0.36$.

The primary outcome was changed to a count of the number of adults diagnosed and treated with TB at the cluster-level. The new primary outcome better reflects the intended effect of the multi-component intervention to drive more people who present to health facilities through the entire TB diagnostic evaluation cascade of care, including being screened for TB, tested for TB (if screen-positive), diagnosed with TB (if tested) and initiated on treatment (if diagnosed). Process re-design is expected to help improve the number screened and tested. Onsite molecular testing is expected to increase the numbers diagnosed (increased sensitivity) and treated (faster turn-around time and reduced workload). Performance feedback is expected to maintain improvement along each step of the cascade. Thus, the intervention is expected to increase both the number of patients entering and completing the cascade of care.

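### TB treatment starts outside the study-site register count as untreated, and no analysis uses the six-month treatment status that could show how many there are

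*Combined protocol and SAP*

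**What the plan says.** All references are to the amended protocol and the amended SAP.

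- **Treated status and date.** SAP 3.4 defines the number treated as "Number of eligible patients entered into the NTLP Treatment register as having started Category I or II regimen". Time-to-treatment runs from the date enrolled to the "treatment start date entered into NTLP Treatment register if treatment start date is within six months of enrolment". The primary numerator is "Number diagnosed and time-to-treatment within 14 days", with no denominator.
- **Whose register.** The treatment definition does not say. The definition of number enrolled in the same section refers to the "GeneXpert laboratory requisition forms and NTLP Treatment register at each study site". SAP 2.3 states: "These endpoints will be evaluated through review of TB registers and GeneXpert machine data for all patients initiating TB evaluation at participating health centers". Under Patient-level data collection in the protocol, health center staff photograph their own registers. Outside treatment centers are contacted only about rifampicin-resistant patients, who do not contribute to the primary analysis.
- **Six-month follow-up.** The protocol has staff telephone all eligible patients, with a home visit if needed, "to assess vital status, diagnostic and treatment status, HIV status, and ART status".
- **Use of that follow-up.** In SAP 3.4 a traced death counts towards mortality. No treatment outcome draws on tracing. The two sensitivity analyses of the primary outcome in SAP 4.4.3 both concern trace-positive Ultra results. Annex Table 3 lists treatment status by arm, but from record review and facility follow-up.

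**The concern.** Under these definitions a confirmed patient who was never treated and one who was treated at another facility look the same: neither is in the study-site register. The two arms may not be equally exposed to this. The intervention is designed to start treatment at the same clinic at the first visit. The control pathway can take up to four visits, and the SAP itself expects more control patients to be lost before treatment.

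If some of those lost patients start promptly elsewhere, part of the measured gain would be a change in where treatment is registered, not more people treated. SAP 3.5 justifies the count outcome as reflecting passage through the whole cascade, including starting treatment, so the distinction bears on interpretation. The same issue affects the other treated-for-confirmed-TB rows in Annex Table 5b.

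**Working it through.** **The plan's own figures.** SAP 3.5 takes 1000 people at 10% prevalence, sensitivity 95% against 40%, and pre-treatment loss 7% against 30%.
- Intervention: 95 × 0.93 = 88.35 starts. Control: 40 × 0.70 = 28 starts. The difference is 6.0 points, as stated.
- The detectable ratios also reproduce. The formula is exp[(z₀.₉₇₅ + z_power) × SD × √(2/9)], with nine effective clusters per arm because one of the ten is the allowance for stratification. It gives 1.302 and 1.357 at SD 0.2, and 1.486 and 1.582 at SD 0.3. The SAP states 1.30, 1.36, 1.49 and 1.58.

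**Two sets of inputs, both from SAP 3.5.**
- A: 95 against 40 diagnosed; loss 7% against 30%.
- B: twice as many diagnosed (80 against 40); loss 15% against 30%. The SAP says less than 15%, so 15% gives the smallest gap between arms.

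**Assumption.** Let D be the number diagnosed, L the loss before treatment, and f the share of lost patients who start elsewhere within 14 days. The documents give no value for f, so it is varied from 0 to 1 and first taken as equal in both arms. L is read as loss from the study-site register.
- Registered starts = D(1 − L)
- All starts within 14 days = D(1 − L + Lf)
- Inflation of the ratio = [(1 − L_I)/(1 − L_I + L_I f)] ÷ [(1 − L_C)/(1 − L_C + L_C f)]

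Example, A at f = 10%: (0.93/0.937) ÷ (0.70/0.73) = 0.9925 ÷ 0.9589 = 1.035.

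| f | Inflation, A | Inflation, B | Planned ratio with all starts counted, A | Same, B |
|---|---|---|---|---|
| 0 | 1.00 | 1.00 | 3.16 | 2.43 |
| 10% | 1.035 | 1.025 | 3.05 | 2.37 |
| 25% | 1.087 | 1.060 | 2.90 | 2.29 |
| 50% | 1.170 | 1.116 | 2.70 | 2.18 |
| 100% | 1.329 | 1.214 | 2.38 | 2.00 |

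**Near the smallest detectable effect.** An observed ratio of 1.30 divided by the inflation factor becomes 1.26 (A) or 1.27 (B) at f = 10%, 1.20 or 1.23 at 25%, and 1.11 or 1.17 at 50%.

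**Unequal f.** The inflation factor equals 1 when f_I/f_C = [L_C/(1 − L_C)] ÷ [L_I/(1 − L_I)]. That is 0.4286/0.0753 = 5.7 for A and 0.4286/0.1765 = 2.4 for B. The direction reverses only if the intervention-arm share exceeds the control-arm share by more than that multiple.

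**Missed starts as numbers.** Missed starts are D × L × f. Per 1000 evaluated at f = 1, they are 6.65 intervention against 12.0 control for A, and 12.0 against 12.0 for B. If 95 diagnosed is paired with 15% loss, they are 14.25 against 12.0.

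**The case against.** A reader might infer that the register-only count does miss more control starts and so favours the intervention, or that much of the measured gain is relocation of treatment. The documents do not support either statement.

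- They do not say how many patients start elsewhere or whether this differs by arm. The direction rests on the expected losses, a non-zero f, and an f that is not far higher in the intervention arm.
- As an absolute number, missed starts need not be larger in control, because the intervention arm diagnoses more patients. The point holds for the share of each arm's starts, which is what a ratio reflects.
- Treatment at the Xpert hub is not described. The protocol sends the specimen to the hub and asks the patient to return to the clinic; the SAP has results come back with sample transport.
- The SAP notes that control diagnosis can take 7 to 10 days, which leaves little time to start elsewhere by day 14. A large f is not documented.

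The trial is also openly pragmatic and register-based. Health centers are telephoned after each two-week extraction to resolve missing information, and other sources are checked. These steps improve the completeness of study-site records, but they do not provide for capturing starts at other facilities.

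Finally, the protocol says that follow-up records treatment status. It mentions neither a start date nor the treating facility. That limit stands, and it is why the proposed analysis needs bounds and can only be supportive.

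**Conclusion.** The textual point holds. Starts outside the study-site register are scored as untreated, and the six-month treatment status enters no treatment outcome or sensitivity analysis, although tracing is used for deaths. Reading the register as the study site's own rests on the number-enrolled definition, SAP 2.3 and the data-collection procedures, because the treatment definition does not say so.

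Inflation of the rate ratio is possible, and it is the likelier direction given the expected losses, but it is not established. With equal f it is nil at f = 0, 2.5% to 3.5% at f = 10%, and 12% to 17% at f = 50%. The planned ratio stays at 2.0 or more even at f = 100%, above the largest tabulated detectable ratio of 1.58. The planned effect is therefore not put in doubt. What is at stake is how large the effect is, and whether it means more people treated or more people treated at the study clinic. This would matter most if the observed ratio were near 1.30.

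**What to change.** Keep the register-based primary analysis.

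1. In SAP 3.4, state whether treatment starts at other facilities count.
2. In SAP 4.4.3 and Annex Table 5a, add a sensitivity analysis that also counts patients with confirmed TB whose six-month follow-up reports treatment begun outside the study-site register. Use the start date where one was recorded. Where it was not, give two bounds: all such starts within 14 days of the date enrolled, and none.
3. Report by arm how many confirmed patients absent from the register were treated elsewhere, never treated, or not traced.

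The cost is SAP wording, a check of what the follow-up form recorded, further runs of the existing model for the two bounds, and one table. The downside is that the data are recalled and incompletely traced, possibly to different degrees by arm, and may lack dates and facilities. The result should be labelled supportive only.

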- **Number with suspected RIF resistant TB:** Number of eligible patients with RIF resistance identified by Xpert testing entered into the GxAlert database, GeneXpert laboratory requisition forms, and/or NTLP Laboratory registers within 6 months of *date enrolled*.
- **Number with confirmed RIF resistant TB:** Number of eligible patients with RIF resistance identified by Xpert testing entered into the GxAlert database, GeneXpert laboratory requisition forms, and/or NTLP Laboratory registers, and RIF resistance confirmed by culture-based DST or a second molecular assay as determined by review of Lab Register at MDR treatment center within 6 months of *date enrolled*.

- **Number treated:** Number of eligible patients entered into the NTLP Treatment register as having started Category I or II regimen, or started on MDR treatment at the MDR treatment center as determined by review of Treatment Register at MDR treatment center within 6 months of *date enrolled*.
- **Number completing treatment:** *Number treated* and with a treatment outcome of cured or completed entered into the NTLP Treatment register or indicated by MDR treatment center staff through direct follow up.
- **Number died:** *Number treated* and with a treatment outcome of died entered into the NTLP Treatment register within 6 months of *date enrolled*, or number eligible with outcome entered as died on direct follow-up form.
- **Time-to-diagnosis:** Number of days from *date enrolled* to earliest date of positive smear or Xpert result recorded in NTLP Laboratory register, GeneXpert laboratory requisition form, NTLP treatment register, or GxAlert database within 6 months of *date enrolled*.
- **Time-to-treatment:** Number of days from *date enrolled* to treatment start date entered into NTLP Treatment register if treatment start date is within 6 months of *date enrolled*.

I. Primary Outcome (Effectiveness)

Outcome	Numerator	Denominator
Number treated for microbiologically-confirmed TB within two weeks of referral for sputum-based testing	Number diagnosed and time-to-treatment within 14 days	None

II. Secondary Outcomes (Effectiveness)

	A. Testing		
Outcome		Numerator	Denominator
Number referred for TB testing		Number referred for testing	None
Proportion completing testing		Number completing testing	Number referred for testing
	B. Diagnosis		
Outcome		Numerator	Denominator
Number diagnosed with microbiologically-confirmed TB*		Number diagnosed	None

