- **Number diagnosed:** Number of eligible patients with microbiologically-confirmed TB via a positive smear and/or valid Xpert test result entered into the NTLP Presumptive TB register, NTLP Laboratory register, GeneXpert laboratory requisition forms, NTLP treatment register, and/or GxAlert database within 6 months of *date enrolled*.
- **Number with suspected RIF resistant TB:** Number of eligible patients with RIF resistance identified by Xpert testing entered into the GxAlert database, GeneXpert laboratory requisition forms, and/or NTLP Laboratory registers within 6 months of *date enrolled*.
- **Number with confirmed RIF resistant TB:** Number of eligible patients with RIF resistance identified by Xpert testing entered into the GxAlert database, GeneXpert laboratory requisition forms, and/or NTLP Laboratory registers, and RIF resistance confirmed by culture-based DST or a second molecular assay as determined by review of Lab Register at MDR treatment center within 6 months of *date enrolled*.
- **Number treated:** Number of eligible patients entered into the NTLP Treatment register as having started Category I or II regimen, or started on MDR treatment at the MDR treatment center as determined by review of Treatment Register at MDR treatment center within 6 months of *date enrolled*.
- **Number completing treatment:** *Number treated* and with a treatment outcome of cured or completed entered into the NTLP Treatment register or indicated by MDR treatment center staff through direct follow up.
- **Number died:** *Number treated* and with a treatment outcome of died entered into the NTLP Treatment register within 6 months of *date enrolled*, or number eligible with treatment outcome entered as died on direct follow-up form.
- **Time-to-diagnosis:** Number of days from *date enrolled* to earliest date of positive smear or valid Xpert result recorded in NTLP Presumptive TB register, NTLP Laboratory register, GeneXpert laboratory requisition form, NTLP treatment register, or GxAlert database within 6 months of *date enrolled*.
- **Time-to-treatment:** Number of days from *date enrolled* to treatment start date entered into NTLP Treatment register if treatment start date is within 6 months of *date enrolled*.

Primary Outcome

Outcome	Numerator	Denominator
Number treated for microbiologically-confirmed TB within 14 days of referral for sputum-based testing	Number diagnosed and time-to-treatment within 14 days	None

Secondary Outcomes

A. Testing		

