Number with RIF resistance detected by Xpert/number with RIF resistance confirmed by culture*	Number with RIF resistance detected by Xpert/number with RIF resistance confirmed by culture	None
Proportion with RIF resistance detected by Xpert/proportion with RIF resistance confirmed by culture*	Number with RIF resistance detected by Xpert/number with RIF resistance confirmed by culture	Number enrolled
Time to microbiologically-confirmed TB**	Time-to-diagnosis if microbiologically-confirmed TB	None
C. Treatment		
Outcome	Numerator	Denominator
Number treated for TB*	Number treated	None
Proportion treated for TB*	Number treated	Number enrolled
Number treated for microbiologically-confirmed TB*	Number diagnosed AND treated	None
Proportion treated for microbiologically-confirmed TB*	Number diagnosed AND treated	Number enrolled
Proportion with microbiologically-confirmed TB treated*	Number diagnosed AND treated	Number diagnosed
Time-to-treatment of microbiologically-confirmed TB	Time-to-treatment if microbiologically-confirmed TB and treated	None
D. Follow-up		
Outcome	Numerator	Denominator
Number with microbiologically-confirmed TB completing treatment	Number diagnosed AND completing treatment	None
Proportion with microbiologically-confirmed TB completing treatment	Number diagnosed AND completing treatment	Number diagnosed AND treated
Number who died within 6 months	Number died	None

Proportion who died within 6 months***	Number died	Number enrolled
Number who died within 6 months	Number diagnosed AND died	None
Proportion who died within 6 months***	Number diagnosed AND died	Number diagnosed
Number who died within 6 months	Number treated AND died	None
Proportion who died within 6 months***	Number treated AND died	Number treated

*Outcome will be assessed within 1 day and within 14 days of enrolment. One day was chosen because the intervention focuses on same-day diagnosis and treatment. 14 days was chosen because the diagnostic process could take 7-10 days in the control arm depending on the frequency of sample transport to Xpert testing sites.

**For the control arm, missing Xpert result dates will be recorded as the next scheduled date of sputum transportation from the health center to the GeneXpert facility (results from the previous batch of testing are returned when the next batch of samples are picked up). For the intervention arm, missing Xpert result dates will be recorded as the day following sample collection.

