***Vital status will be assessed between 4-9 months from enrolment

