Pre-specified sub-group analyses for a subset of secondary outcomes will be conducted to assess whether the effect of the intervention differs between sub-groups. The sub-groups are (1) HIV status at enrolment (self-reported, laboratory test resulted as noted on primary data sources, or through pre-ART and ART register data extraction) defined as positive or negative, and (2) sex (male or female). The effect of the intervention will be estimated for each sub-group, and P-values for effect modification, appropriate for individual-level covariates, will be reported.¹⁰ These sub-group analyses will be conducted for the following secondary outcomes: proportion completing testing; proportion of patients referred for TB testing who are diagnosed with microbiologically-confirmed TB within 14 days; proportion of patients with microbiologically-confirmed TB who are treated within 14 days of referral for sputum-based testing; and the proportion who died within 6 months. See Annex table 5c. Results from subgroup analyses will also be summarised as forest plots.

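### The all-eligible death count sets no six-month limit on traced deaths, although its rows are labelled as six-month mortality and contact may be as late as month 9

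*Combined protocol and SAP*

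**What the plan says.** The current SAP (the amended version), section 3.4, defines three death counts.

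- **Treated patients.** A register death within six months of enrolment, or "number treated and confirmed dead by next of kin with a date of death within six months of enrolment".
- **Confirmed-TB patients.** The same two branches with the same six-month date condition, applied to diagnosed patients.
- **All eligible patients.** A register death in a treated patient within six months, "or number traced with a death recorded". The second branch has no time limit.

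The Follow-up block of the secondary outcomes table reports all three as a number and as a proportion under identical labels. The proportion is "Proportion who died within 6 months", and its denominator for the all-eligible count is number enrolled. The footnote to the proportion rows reads: "Vital status will be assessed between 4-9 months from enrolment".

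The protocol places the vital-status call at six months after the first visit. Section 2.3 of the SAP says of any difference between the two documents: "however, this analysis plan takes precedence". Section 4.4.5 lists mortality among the sub-group outcomes ("and the proportion who died within 6 months") without saying which of the three proportions is meant.

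**The concern.** A row's label and the rule that produces its number should give the same time horizon. Here the label says six months, while the tracing branch counts any death known at a contact that may fall in month 7, 8 or 9. The sibling rows, under the same label, exclude those deaths. Two analysts could derive different all-eligible figures from the same data, one following the definition and the other the label.

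At stake are the reported level of six-month mortality in the whole enrolled population and its agreement with the two narrower mortality rows.

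**Working it through.** **Is the limit restored elsewhere?**

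| Place | Branch for traced or followed-up deaths | Date limit |
|---|---|---|
| Current SAP 3.4, treated | "number treated and confirmed dead by next of kin with a date of death within six months of enrolment" | yes |
| Current SAP 3.4, confirmed TB | same condition, diagnosed patients | yes |
| Current SAP 3.4, all eligible | "or number traced with a death recorded" | none |
| Protocol, Outcomes, Definitions | "or number eligible with outcome entered as died on direct follow-up form" | none |
| SAP version 1.0, 3.4 (superseded) | "or number eligible with treatment outcome entered as died on direct follow-up form" | none |

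No other passage supplies one. The SAP amendment table dates both the all-eligible definition and the 4 to 9 month window to 21 November 2019, so the open branch and the late contact belong to the same current plan.

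**Test case.** Take a treated patient with no register death inside six months, contacted in month 9 and reported to have died in month 8. In the all-eligible row the tracing branch is met, so the patient counts as dead. In the treated row the date condition fails, so the patient does not. Both rows carry the six-month label.

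**Size.** The documents give no mortality rate and no expected number of deaths, so there is no stated figure to reproduce. All inputs below are assumptions: six-month risk 5%, every patient traced once, the register branch ignored, and contact month c spread evenly over 4 to 9.

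- Cumulative risk: F(t) = 1 − exp(−H·(t/6)^s), with H = −ln(0.95) = 0.0513. Shape s = 1 is a constant hazard; s = 0.5 is front-loaded.
- Rule as written: mean of F(c) ÷ 0.05.
- With the date limit: mean of F(min(c, 6)) ÷ 0.05.
- Late share: the difference between the two means ÷ mean of F(c).

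| | s = 1 | s = 0.5 |
|---|---|---|
| Risk counted as written | 5.40% | 5.17% |
| Relative to true 5% | 1.080 | 1.033 |
| Risk counted with date limit | 4.67% | 4.83% |
| Relative to true 5% | 0.935 | 0.965 |
| Share of counted deaths after month 6 | 13.4% | 6.5% |

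The excess as written is smaller than the late share because patients contacted alive in months 4 to 6 may die before month 6 uncounted. The date limit removes the late deaths but not that shortfall.

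**Other contact patterns** (as written, then with the limit, relative to the true risk):

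- Contacts peaking at month 6 within 4 to 9: 1.053 and 0.956 (s = 1); 1.023 and 0.977 (s = 0.5).
- Contacts even over months 5 to 7: 1.000 and 0.959 (s = 1); 0.999 and 0.979 (s = 0.5).

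**Between arms.**

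- With equal timing, even over months 4 to 9, true risks of 4% and 5% (ratio 0.80) are returned as 0.8006 (s = 1) or 0.8002 (s = 0.5).
- As a hypothetical only, let one arm be contacted over months 5 to 9 and the other over 4 to 8, with a true ratio of 1. The rule as written gives 1.16 (s = 1) or 1.08 (s = 0.5); with the date limit it gives 1.07 or 1.03.

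**Undated deaths.** Of deaths found at contacts even over months 6 to 9, the share that fell within six months is 0.05 ÷ mean of F(c), which is 0.81 (s = 1) or 0.90 (s = 0.5).

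**The case against.** *The label already settles it.* An analyst reading label and numerator together, with two sibling definitions that carry the limit, might well apply it. The omission is probably one of drafting. That stands as a likely account of intent, but a definition in a SAP should not need the inference.

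*The sentence may be unfinished.* It is the only one of the three without a closing full stop, so truncation is possible. It is not shown: the phrase is grammatically complete, and the protocol and SAP version 1.0 also set no limit. Those two texts are weak evidence of intent, since they went with a call at six months, where a limit mattered less.

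*The limit does not reliably bring the level closer to the truth.* This stands. In the six scenarios above, the error with the limit is smaller in two (constant hazard, contacts over months 4 to 9), about equal in one and larger in three. The case for the limit is that the number then matches its label and its siblings and depends less on when contact was made.

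*The comparison between arms is biased.* A reader might infer this from the late contacts. The documents do not support it: the protocol sets one tracing procedure for all patients, nothing shows timing that differs by arm, and with equal timing the ratio is unchanged to two decimals.

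*Dates of death may not exist.* This also stands. The documents require a date of death only for treated or diagnosed patients. The protocol's definition mentions only an outcome of died on the follow-up form. A rule for undated deaths is therefore part of the fix.

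**Conclusion.** The point holds as an inconsistency between a definition, its label and its two sibling definitions. As written, the all-eligible count admits traced deaths from months 7 to 9 into a six-month row.

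Under the assumed 5% risk with contacts even over months 4 to 9, about 7% to 13% of counted deaths would be late and the level would read 1.03 to 1.08 times the true risk. With the limit it would read 0.935 to 0.965. These figures rest wholly on assumed inputs and only show scale.

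The documents do not support reading this as a biased treatment comparison, nor do the calculations support reading the limit as a cure for the level. It is minor: one secondary outcome, reported as a count and a proportion and possibly used in the HIV and sex sub-group analyses. The primary outcome is unaffected.

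**What to change.** 1. In the current SAP, section 3.4, reword the tracing branch of the all-eligible count so that it takes patients traced and confirmed dead whose death is dated no more than six months after enrolment. Apply this to both the number and the proportion.
2. State one rule for confirmed deaths of unknown date. For example, count them if contact was at or before six months; for later contacts fix one rule in advance and run a sensitivity analysis the other way.

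The cost is one phrase, one added rule, a re-derived death indicator and one sensitivity analysis. The uncertain part is data: if dates of death were not recorded for enrolled patients who were neither treated nor diagnosed, the undated-death rule will decide more of the result. No trial procedure changes.
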